1. INTRODUCTION

1.1 STUDY OBJECTIVES

1.1.1 Primary Objective

- To determine whether unilateral adrenalectomy in patients diagnosed with subclinical hypercortisolism and an adrenal neoplasm results in normalization and/or improvement of hypertension as assessed by reduction in pharmacotherapy and/or normalization of blood pressure (systolic pressure ≤ 140 and diastolic pressure ≤ 90), diabetes as assessed by reduction or elimination of pharmacotherapy and/or improvement in A₁C to $< 6.5\%$, osteoporosis by increase in bone formation markers indicative of increased bone formation, hypercholesterolemia as assessed by a reduction or elimination of pharmacotherapy and/or reduction in LDL levels to risk-stratified goal levels as defined by ATP III, and/or overweight or obesity as assessed by a 10 percent reduction in weight at 6 months.

1.1.2 Secondary Objectives:

- To determine the risk of primary adrenal malignancy in patients with subclinical hypercortisolism and adrenal mass less than 5 cm.
- To determine whether FDG PET/CT scan is diagnostic of subclinical hypercortisolism.
- To determine the optimal diagnostic test for subclinical hypercortisolism.
- To determine whether patients show an improvement in quality of life after adrenalectomy compared to medical therapy.
- To determine whether patients have an increased risk of deep venous thrombosis with subclinical hypercortisolism, regardless of treatment.
- To determine whether dermal thickness is diagnostic of subclinical hypercortisolism.
- To determine whether ultrasound of the skin is diagnostic and is able to show resolution of subclinical hypercortisolism after adrenalectomy.

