2.4 RANDOMIZATION (OR STRATIFICATION) PROCEDURES

Patients with subclinical hypercortisolism will be randomized to adrenalectomy or observation as defined above and followed for 6 months. At the end of 6 months, the patients who were in the observation-only arm will all be offered an adrenalectomy. Patients with subclinical hypercortisolism tend to have high prevalence of metabolic consequences, specifically hypertension, diabetes, osteoporosis, hypercholesterolemia, and/or obesity. The patients will be randomized by the CRO.

To be conservative, the primary goal of this study will be to determine if the use of adrenalectomy is associated with 35% improvement vs. 5% improvement over 6 months without surgery as defined for any one or more of the following associated metabolic complications: hypertension, diabetes, osteoporosis, hypercholesterolemia, and/or obesity. With 31 patients per arm (62 total), there would be 80% power to detect a difference of this magnitude using a 0.05 significance level two-tailed Fisher's exact test.

Abbreviated Title: Subclinical Hypercortisolism**Version Date: 12/19/2016**

The following definitions will be used to determine if a given metabolic complication shows sufficient improvement in order to be considered as a component of a successful outcome:

Hypertension: normalization and/or improvement in blood pressure as assessed by reduction in pharmacotherapy and/or normalization of blood pressure (systolic pressure ≤ 140 and diastolic pressure ≤ 90) from baseline.

Diabetes: normalization and/or improvement in diabetes as assessed by normalization (A1C $< 6.5\%$), and/or reduction and/or discontinuation of pharmacotherapy.

Osteoporosis: an increase in the level of bone formation markers greater than the least significant change, which is calculated by multiplying the “precision error” of the specific biomarker by 2.77 (95% confidence interval) as per the National Osteoporosis Foundation (NOF) Clinician’s Guide to Prevention and Treatment of Osteoporosis 2013 ([Appendix D](#)).

Hypercholesterolemia: improvement in cholesterol as assessed by a reduction or elimination of pharmacotherapy and/or reduction in LDL levels to the optimal risk stratified goal as defined by ATP III guidelines ([Appendix E](#)).

Obesity: improvement in obesity as defined by a ten percent reduction in fasting morning weight compared to baseline.

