2.5.7.12 Fasting Triglyceride, total cholesterol, LDL, HDL levels

3 STUDY IMPLEMENTATION

3.1 STUDY DESIGN

This is a prospective randomized study of individuals with an adrenal mass less than or equal to 5 cm with biochemically confirmed hypercortisolism (2 out of 3: DST >3 mmol/l, elevated urine free cortisol, and/or morning ACTH <2.2 pmol/l) without overt clinical signs and/or symptoms (facial plethora, easy bruising, violaceous striae, and/or proximal muscle weakness) of excess cortisol. Individuals will undergo a clinical work up for an adrenal mass including laboratory and radiological studies (see below). Patients diagnosed with subclinical hypercortisolism and an adrenal mass less than 5 cm will be randomly assigned to either the non-operative or operative arm of the study. In patients found to have bilateral adrenal masses, the larger of the two masses will be treated as the adrenal lesion responsible for subclinical hypercortisolism. These patients with bilateral adrenal masses will be randomly assigned to either the non-operative or operative arm of the study. The responsible lesion will be adrenal mass that will be removed with a unilateral adrenalectomy or monitored. For patients in the non-operative or medical treatment-only arm, baseline evaluation will be undertaken, as well as follow up and re-evaluation every 3 months for 6 months, after which they will crossover to the operative arm and undergo an adrenalectomy. If a patient develops overt signs and symptoms of cortisol excess during the 6 months of observation, the tumor grows after enrollment during the 6 months of observation or 6 months have elapsed, the patient will cross over to the operative arm, and undergo an adrenalectomy. Worsening of metabolic complications will not be an indication for crossover. Patients after crossing over to the operative arm will have follow up every 3, 6, 9, and 12 months for the first year, six month follow up thereafter for the second year, and yearly follow up thereafter for three years. For a patient in the operative arm, the patient will undergo baseline evaluation, adrenalectomy, and follow up every 3, 6, 9, and 12 months for the first year, six month follow up thereafter for the second year, and yearly follow up thereafter for three years. At each follow-up visit, the patient will undergo repeat radiological and laboratory evaluation (see [Table 1](#)). Uniformity of medical management will be ensured by coordinating with primary care physicians, endocrinologists and the utilization of national guidelines in treating the metabolic manifestations and consequences of subclinical hypercortisolism.

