
Table 1

Abbreviated Title: Subclinical Hypercortisolism**Version Date: 12/19/2016****3.2 QUESTIONNAIRES**

The questionnaires to be utilized include the generic SF-36 and the Cushing specific quality of life questionnaire (26). The questionnaires will assess the patient's quality of life preoperatively and postoperatively. The questionnaires will take approximately ten minutes to complete. The SF-36 form will be given first, and the Cushing's specific quality of life questionnaire will follow. The topics will address general health and wellbeing. After the questionnaires are collected and entered into a computer database, the data will be shredded.

*Abbreviated Title: Subclinical Hypercortisolism**Version Date: 12/19/2016***3.3 STUDY CALENDAR****3.3.1 Operative Arm**

Baseline and Follow-up Testing for Operative Arm					
Test	Baseline evaluation (MO)	3 monthly evaluation (M3)	3 monthly evaluation (M6, M9)	6 monthly evaluation (M12, M18)	12 monthly evaluation (M24, M36, M48, M60)
QoL Questionnaire	x	x		x	
CT adrenal	x				
FDG PET/CT scan	x				
DEXA	x			x	x
Duplex	x	x			
Vertebral (X-rays) morphometry and body composition	x	x	x		
Skin ultrasound	x	x	x	x	x
CBC	x	x	x	x	x
Chemistries	x	x	x	x	x
PT/PTT/INR	x				
Renin/PAC	x				
24 hour urine free cortisol	x	x			
midnight serum/salivary cortisol	x	x			
baseline serum cortisol	x	x			
DST	x	x			
plasma ACTH	x	x			
serum fractionated plasma normetanephrines and metanephrines	x				
24-hour urinary epinephrine, dopamine, norepinephrine, and fractionated normetanephrines and metanephrines	x				
DHEA	x	x	x	x	
Urinary 17 ketosteroids	x	x	x	x	x
testosterone	x	x			
24 hour urinary calcium, phosphorous,	x	x	x	x	x

*Abbreviated Title: Subclinical Hypercortisolism**Version Date: 12/19/2016*

Baseline and Follow-up Testing for Operative Arm					
Test	Baseline evaluation (MO)	3 monthly evaluation (M3)	3 monthly evaluation (M6, M9)	6 monthly evaluation (M12, M18)	12 monthly evaluation (M24, M36, M48, M60)
amino acid random urine					
25-OH Vitamin D Level	x	x	x	x	x
PTH	x	x			
fasting glucose	x	x	x	x	x
A ₁ C	x	x	x	x	x
Triglyceride, total LDL, HDL levels	x	x	x	x	x
NIH Advanced Directives Form¹	x				

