3.3.2 Non-Operative Arm

Baseline and Follow-up Testing for Non-Operative Arm						
Test	Baseline evaluation (MO)	Preop 3 monthly evaluation (M3, M6)	3 monthly evaluation (M9)	3 monthly evaluation (M12, M15)	6 monthly evaluation (M18, M24)	12 monthly evaluation (M30, M42, M54, M66)
QoL Questionnaire	x	x	x		x	
CT adrenal	x	x				
FDG PET/CT scan	x					
DEXA	x				x	x
Duplex	x	x	x			
Vertebral (X-rays) morphometry and body composition	x		x	x		
Skin ultrasound	x	x	x	x	x	x
CBC	x	x	x	x	x	x
Chemistries	x	x	x	x	x	x
PT/PTT/INR	x					
Renin/PAC	x					

*Abbreviated Title: Subclinical Hypercortisolism**Version Date: 12/19/2016*

Baseline and Follow-up Testing for Non-Operative Arm						
Test	Baseline evaluation (MO)	Preop 3 monthly evaluation (M3, M6)	3 monthly evaluation (M9)	3 monthly evaluation (M12, M15)	6 monthly evaluation (M18, M24)	12 monthly evaluation (M30, M42, M54, M66)
24 hour urine free cortisol	x	x	x			
midnight serum/salivary cortisol	x	x	x			
baseline serum cortisol	x	x	x			
DST	x	x	x			
plasma ACTH	x	x	x			
serum fractionated plasma normetanephrines and metanephrines	x	x				
24-hour urinary epinephrine, dopamine, norepinephrine, and fractionated normetanephrines and metanephrines	x	x				
DHEA	x	x	x	x	x	
Urinary 17 ketosteroids	x	x	x	x	x	x
testosterone	x	x	x			
24 hour urinary calcium, phosphorous, amino acid random urine	x	x	x	x	x	x
25-OH Vitamin D Level	x	x	x	x	x	x
PTH	x	x	x			
fasting glucose	x	x	x	x	x	x
A ₁ C	x	x	x	x	x	x
Triglyceride, total LDL, HDL levels	x	x	x	x	x	x

Abbreviated Title: Subclinical Hypercortisolism

Version Date: 12/19/2016

Baseline and Follow-up Testing for Non-Operative Arm						
Test	Baseline evaluation (MO)	Preop 3 monthly evaluation (M3, M6)	3 monthly evaluation (M9)	3 monthly evaluation (M12, M15)	6 monthly evaluation (M18, M24)	12 monthly evaluation (M30, M42, M54, M66)
NIH Advanced Directives Form¹						

¹ As indicated in section 10.3, all subjects will be offered the opportunity to complete an NIH advanced directives form. This should be done preferably at baseline but can be done at any time during the study as long as the capacity to do so is retained. The completion of the form is strongly recommended, but is not required.

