7 STATISTICAL CONSIDERATIONS

The primary objective of this study is to determine if the use of unilateral adrenalectomy is associated with normalization and/or improvement of hypertension, diabetes, osteoporosis, hypercholesterolemia, and/or obesity compared to medical treatment-only arm.

Patients with subclinical hypercortisolism will be randomized to adrenalectomy or medical treatment as defined above and followed for 6 months. At the end of 6 months, the patients who were in the medical treatment-only arm will all be offered an adrenalectomy. Patients with subclinical hypercortisolism tend to have high prevalence of metabolic consequences, specifically hypertension, diabetes, obesity and/or osteoporosis.

To be conservative, the primary goal of this study will be to determine if the use of adrenalectomy is associated with 35% who have improvement vs. 5% who improve over 6 months without surgery as defined for any one or more of the following associated complications: hypertension, diabetes, osteoporosis, hypercholesterolemia, and/or obesity. With 31 patients per arm (62 total), there would be 80% power to detect a difference of this magnitude using a 0.05 significance level two-tailed Fisher's exact test.

For the potential 31 patients initially randomized to observation and then undergoing an adrenalectomy at 6 months, the level of MAP, systolic, and diastolic pressure at 6 months but just before surgery will be compared to these values in the potential 31 patients initially randomized to immediate adrenalectomy 6 months after surgery using a Wilcoxon rank sum test. In addition, in the patients initially randomized to observation the changes in MAP from baseline to 6 months of observation as well as the declines in systolic and diastolic pressure from 6 months of observation until 6 months after surgery will be compared with a Wilcoxon signed rank test. Other important continuous parameters such as change in weight, triglycerides, total, HDL and LDL cholesterol, A1c, fasting glucose, and bone density may also be compared within patients using Wilcoxon signed rank test.

Abbreviated Title: Subclinical Hypercortisolism

Version Date: 12/19/2016

It is expected that 15-20 eligible patients may be able to enroll on this trial per year. In order to enroll 62 evaluable patients, it is anticipated that 3-4 years would be required. In order to allow for a small number of inevaluable patients, the accrual ceiling will be set at 66 patients.

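### Quality of life is compared between randomised arms at M3 only; adding the questionnaires to the operative-arm 6-month visit would give a second comparison, at the end of the controlled period

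*Combined protocol and SAP*

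**What the plan says.** Section 1.1.2 sets a comparative aim: "To determine whether patients show an improvement in quality of life after adrenalectomy compared to medical therapy". Section 1.2 gives the reason: the earlier comparison of operated and observed patients was not randomised, and a randomised population would help.

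Section 3.2 describes the purpose of the two questionnaires as assessing "quality of life preoperatively and postoperatively. The questionnaires will take approximately ten minutes to complete". It gives no months. These are set by the study calendars:

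- Operative arm (3.3.1): the quality-of-life row is marked at baseline, at M3 and in the M12/M18 column. It is blank in the column headed "3 monthly evaluation (M6, M9)" and in the yearly column from M24.
- Non-operative arm (3.3.2): the row is marked at baseline, in the column headed "Preop 3 monthly evaluation (M3, M6)", at M9 and in the M18/M24 column. It is blank in the M12/M15 column and in the yearly column from M30.

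Section 3.1 gives non-operative patients "follow up and re-evaluation every 3 months for 6 months, after which they will crossover to the operative arm". Section 2.4 words the same step as an offer: "At the end of 6 months, the patients who were in the observation-only arm will all be offered an adrenalectomy".

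Section 7 specifies no quality-of-life analysis. Its primary comparison covers 6 months. Its between-arm blood-pressure comparison sets observation-arm values at 6 months, just before surgery, against those of patients "initially randomized to immediate adrenalectomy 6 months after surgery using a Wilcoxon rank sum test".

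**The concern.** Only the first 6 months offer a randomised contrast between adrenalectomy and medical treatment. After that, the observation arm is offered surgery, so later scores mainly compare immediate with delayed surgery. Within that window the two calendars share a single follow-up month for quality of life, M3. At M6 the observation half of a between-arm comparison is collected and the operative half is not.

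The plan can therefore show whether the arms differ at M3. It cannot show between arms whether that difference persists, grows or fades by month 6, and the quality-of-life result cannot be set beside the 6-month metabolic and blood-pressure results. Operative-arm scores not collected at 6 months cannot be recovered afterwards.

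**Working it through.** The plan states no sample size, power or test for quality of life, so there is no figure of its own to reproduce. The 80% power in section 7 belongs to the primary endpoint and is not used here. The check is a reading of the calendars followed by a count.

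**Step 1. The quality-of-life rows side by side (3.3.1 and 3.3.2).**

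| Study month | Operative arm | Observation arm | Both arms scored? |
|---|---|---|---|
| M0 | scored | scored | yes (baseline) |
| M3 | scored | scored, before surgery | yes |
| M6 | blank | scored, before surgery | no |
| M9 | blank | scored | no |
| M12 | scored | blank | no |
| M18 | scored | scored | yes, but after the planned crossover |
| M24 | blank | scored | no |

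M3 is the only shared follow-up month before the planned crossover. No other section schedules an operative-arm questionnaire at M6. Table 1, which section 3.1 cites, is not shown in the text available, but it is cited there for radiological and laboratory evaluation, not for questionnaires.

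**Step 2. Why the cell is probably blank.** Assume that operative-arm months run from surgery and that crossover surgery takes place at M6. Months after surgery in the observation arm are then study month minus 6:

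- M9 − 6 = 3, scored
- M12 − 6 = 6 and M15 − 6 = 9, both blank
- M18 − 6 = 12 and M24 − 6 = 18, both scored

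The operative arm is likewise scored at 3, 12 and 18 and blank at 6 and 9. The two schedules match by time since surgery, which fits the before-and-after purpose in section 3.2. On this reading the observation-arm M6 score is the pre-operative value for crossover surgery.

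**Step 3. Count of follow-up scores at months when both arms are scored before crossover.** Inputs: 31 patients per arm (section 7) and full attendance (an assumption).

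- As scheduled, M3 only: 31 + 31 = 62.
- With the operative arm also scored at 6 months: (31 + 31) + (31 + 31) = 124.
- Extra questionnaire occasions needed: 31, all in the operative arm, because the observation-arm M6 scores are already scheduled.

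**Step 4. Burden.** Section 3.2 puts the two questionnaires at about ten minutes.

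- 31 × 10 = 310 minutes, or 310 / 60 = 5.2 hours in total.
- At the accrual ceiling of 66, assuming an equal split, 33 × 10 = 330 minutes, or 5.5 hours.

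**Step 5. Does the visit exist?** Yes. Section 3.1 says of operative-arm patients that "the patient will undergo baseline evaluation, adrenalectomy, and follow up every 3, 6, 9, and 12 months for the first year", section 5.4 has them re-evaluated every 3 months to M12, and the M6/M9 column of 3.3.1 already carries blood tests, skin ultrasound and other assessments.

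**The case against.** The strongest reply is that nothing is broken. The objective sets no month, and section 3.2 promises only assessment before and after surgery. Both arms are scored at baseline and at M3, which is a randomised comparison with a baseline. The blank cell also looks deliberate. Besides the match in step 2, several other rows (duplex, urinary free cortisol, midnight cortisol, dexamethasone suppression, ACTH, testosterone, PTH) are done in the operative arm at M0 and M3 only, but in the observation arm at M3, M6 and M9. All of this stands. It makes the point a design improvement, not a contradiction in the plan.

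M3 also has something in its favour. Under section 3.1, overt signs or tumour growth bring surgery forward, so by month 6 there has been more opportunity for early crossover. This too stands, and it is a reason to analyse as randomised and to keep M3 in the report.

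Finally, the documents do not say whether operative-arm months run from surgery or from randomisation, so a month-6 comparison needs its alignment stated. That is right, but section 7 already provides an alignment for blood pressure that can be reused. On either clock, no operative-arm questionnaire is scheduled at M6.

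A reader might go further and infer any of the following, which the documents do not support:

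- That the objective cannot be tested in a controlled way. It can, at M3.
- That M3 is too early. No section says when quality of life should respond to adrenalectomy, and the earlier comparison cited in section 1.2 is reported at final follow-up without a month.
- That 93 controlled follow-up scores are already scheduled (62 at M3 plus 31 at M6). The 31 observation-arm M6 scores have no operative counterpart, so the between-arm count is 62.
- That the observation-arm M6 scores are wasted. They serve as pre-operative values within patients.

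**Conclusion.** The point holds as a low-cost improvement to one secondary objective. The randomised quality-of-life comparison has one follow-up time, M3, and could have two, the second at the end of the controlled period: 62 follow-up scores at shared months against 124. These counts assume 31 patients per arm and full attendance. At month 6 some observation patients may already have had surgery, so fewer than 31 may still be unoperated.

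What the second time point would add in precision or power cannot be stated, because the plan gives no quality-of-life effect size, power or test for this trial. The primary endpoint, the sample size and the stated 80% power are not affected.

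**What to change.** Split the M6/M9 column for the quality-of-life row in 3.3.1 and mark M6, so that the SF-36 and the Cushing's questionnaire are completed at the existing operative-arm 6-month visit.

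Add to section 7 a short statement that:

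- the 6-month scores are compared between the randomised arms, adjusted for baseline;
- the time alignment is that of the blood-pressure comparison (observation arm at 6 months just before surgery, operative arm 6 months after surgery), with the observation-arm questionnaire completed before crossover surgery;
- patients are analysed as randomised, because some may cross over early;
- the M3 comparison is also reported.

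The same edit should say whether operative-arm months run from surgery or from randomisation.

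The cost is about ten minutes per operative patient, 5.2 hours in total (5.5 hours at the accrual ceiling), plus a little more analysis. No visit or procedure is added. If the calendar is left as it is, one sentence should say that the randomised quality-of-life comparison is at M3 only.

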1.2 BACKGROUND AND RATIONALE

The advent of widespread use of computed tomography has resulted in an increase in detection of incidentally discovered adrenal masses termed adrenal incidentalomas (1). These adrenal incidentalomas have an estimated prevalence of 4-7% in the adult population (2, 3). The prevalence of these masses increases with age: the prevalence is 0.2% in young patients compared to 6.9% in subjects older than 70 years of age (4). The majority of these masses, 65 to 90%, are nonfunctioning adenomas (hormonally inactive). However, the remaining masses are hormonally active and may secrete excess cortisol, aldosterone, androgens, or catecholamines (4). Excess cortisol secretion may manifest as Cushing's syndrome, which is clinically identifiable with specific physical findings such as facial plethora, easy bruising, violaceous striae, and proximal muscle weakness (5). A subset of patients, however, will have biochemical evidence of excess cortisol without these overt clinical signs and/or symptoms. It is estimated approximately 0.6 to 30% of patients with an adrenal incidentaloma and biochemical evidence of abnormal cortisol secretion will manifest in this manner. These patients are diagnosed with subclinical hypercortisolism (2, 3, 6). An estimated prevalence of subclinical hypercortisolism, therefore, in the adult population is between 0.2 and 2.0% (3). The excess cortisol secretion may

Abbreviated Title: Subclinical Hypercortisolism

Version Date: 12/19/2016

lead to metabolic consequences that can adversely affect patients, which may be ameliorated by an adrenalectomy. This study is designed to provide answers to the optimal therapeutic management of patients with an adrenal neoplasm and subclinical hypercortisolism.

One of the major implications of the relative high prevalence of adrenal incidentalomas is the risk of malignancy that these incidentally discovered masses confer regardless of hormonal status. As the US population continues to age, *a priori* the prevalence will continue to increase. One of the most reliable factors that separate benign from malignant masses is size. In one of the largest retrospective studies of incidentally discovered masses, Mantero et. al. demonstrated that size is reliable in predicting malignancy. The retrospective multicenter study evaluated 1,004 patients with adrenal incidentalomas over a 15 year period. Of these 1,004 patients, 380 patients underwent adrenalectomy. Benign adenomas were significantly smaller than carcinomas (median 3.5 cm versus 7.5 cm, $p < 0.001$), and that a cut-off at 4.0 cm had the highest sensitivity (93%) in differentiating benign from malignant tumors. Although at this size cut-off there was poor specificity (42%) and poor positive predictive value (16%), the negative predictive value was 98%. The implication of this study is any adrenal incidentaloma over 4 cm warrants strong consideration towards operative intervention regardless of hormonal status, as the authors recommend. However, if the 5 cm mass size is used as a cut-off, the sensitivity decreases to 81%, but the specificity increases to 63% (7). Due to the increase in specificity and risk of malignancy, we therefore will use 5 cm as our upper limit size threshold for this randomized control trial comparing adrenalectomy to observation as there are no prospective studies which have adequately ascertained risk of malignancy for adrenal incidentalomas. Although hypercortisolism status was not associated with the risk of malignancy, these masses can be functionally active resulting in adverse metabolic consequences. Patients with subclinical hypercortisolism have similar metabolic consequences as Cushing's syndrome such as diabetes, hypertension, dyslipidemia, and osteoporosis, and therefore may also benefit from treatment (8-15). The natural history of subclinical hypercortisolism and the prevalence of these metabolic complications, and the unknown risk of malignancy provides a basis and rationale for potential surgical intervention.

The natural history of subclinical hypercortisolism is associated with progression and consequences of metabolic diseases (3). Studies have shown that cortisol excess may lead to or contribute to long term consequences such as hypertension, diabetes, dyslipidemia, obesity, and osteoporosis (1, 14, 16). In these patients, hypertension has a prevalence of 33% to 89% (8-15, 17), diabetes and/or impaired glucose metabolism has a prevalence of 15 to 66% (8-15, 17, 18), dyslipidemia has a prevalence of 23 to 77% (8, 10-12, 14, 17-18), overweight and/or obesity has a prevalence of 19 to 75% (8, 10-12, 14), and osteoporosis has a prevalence of 30% (10).

Because of the high prevalence of cardiovascular disease in subclinical hypercortisolism in patients with a unilateral adrenal neoplasm some investigators have compared patients with subclinical hypercortisolism with a unilateral adenoma to patients with a nonfunctioning unilateral adrenal neoplasm to assess the consequences and contribution of increased cortisol secretion. A recent large cross-sectional study by Di Dalmazi, et. al., showed patients with subclinical hypercortisolism to have a higher prevalence of type 2 diabetes, coronary heart disease, osteoporosis, and fractures when compared to patients with nonfunctioning adrenal neoplasms. Over a ten year period, 348 eligible patients with an adrenal incidentaloma were included and divided into four groups consisting of patients with nonfunctional adenomas

(n=203), characterized by a cortisol response less than 1.8 µg/dL after the 1 mg dexamethasone suppression test (DST) or as subclinical hypercortisolism (n=19), characterized by a cortisol response to DST of > 5 µg/dL. The remaining patients had an intermediate response to the DST and either urinary free cortisol and/or plasma ACTH that were abnormal (n=71), or normal (n=55). Compared to non-functioning adenomas, those with subclinical hypercortisolism had an increased prevalence of type 2 diabetes (42.1% vs. 15.2%, p<0.01), coronary heart disease (26.3% vs. 2.9%, p<0.01), and osteoporosis (47.3% vs. 14.8%, p<0.01). Although hypertension was highly prevalent in the subclinical hypercortisolism group compared to the nonfunctioning adenoma group (94.7% vs. 73.4%), this was not statistically significant (p=0.173). There was a significant association between coronary heart disease (odds ratio (OR), 6.104; 95% CI, 1.41-26.49, p=0.016), type 2 diabetes (OR, 3.443; 95% CI, 1.181-10.038, p=0.024), osteoporosis (OR, 5.940; 95% CI, 1.793-19.677, p=0.004), and osteoporotic fractures (OR, 6.530; 95% CI, 1.292-32.994, p=0.023) when comparing the subclinical hypercortisolism and nonfunctioning adenoma groups. The data from this study indicates that there is an increased prevalence and association of adverse metabolic and cardiovascular disease in patients with subclinical hypercortisolism (19).

Although Di Dalmazi, et. al. did not find an increased prevalence of hypertension amongst patients with subclinical hypercortisolism compared to nonfunctioning adenomas (19), a recent study by Oki, et. al. clearly demonstrated a higher prevalence of hypertension. The study included 80 patients with adrenal neoplasms and were divided into three groups: nonfunctioning adenomas (n=53), subclinical hypercortisolism (n=13, mildly elevated cortisol following a 1-mg dexamethasone suppression test without any other hypothalamic-pituitary-adrenal (HPA) axis abnormality), and subclinical Cushing's syndrome (n=14, elevated cortisol following a 1-mg dexamethasone suppression test with at least one other HPA axis abnormality). The prevalence of hypertension was clearly increased in the subclinical hypercortisolism (78.6%) and subclinical Cushing's syndrome (84.6%) groups compared to the nonfunctioning group (39.6%) (p=0.002). The investigators assessed the odds of hypertension for subclinical hypercortisolism compared to nonfunctioning adenomas and found an 11.7-fold increased risk (CI 1.9-72.7, p=0.009). Similarly, the odds of hypertension for subclinical Cushing's syndrome compared to nonfunctioning adenomas showed a 9.5-fold increased risk (CI 1.9-48.3, p=0.007). Although the authors did not discuss treatment, *a priori* one would hypothesize adrenalectomy as potentially beneficial in these patients (13).

Another disease process that is affected by hypercortisolism is osteoporosis. A multicenter study in Italy addressed the prevalence of bone mineral density, fracture risk and quality of bone architecture in patients with osteopenia (control), unilateral adrenal incidentalomas with and without subclinical hypercortisolism. Two hundred and eight-seven patients with unilateral adrenal incidentalomas were evaluated for subclinical hypercortisolism, bone mineral density, and spinal fracture. Of these 287 patients, 85 were diagnosed with subclinical hypercortisolism. The study also included a control group of 194 patients without adrenal incidentalomas for comparison. A comparison of patients (n=85) with subclinical hypercortisolism, adrenal incidentaloma patients without subclinical hypercortisolism (n=202), and controls (n=194) revealed a significantly lower bone mineral density (lumbar spine -0.73 ± 1.43 , 0.17 ± 1.33 , 0.12 ± 1.21 , respectively, p=0.0001; femoral neck -0.37 ± 1.06 , 0.07 ± 1.09 , 0.17 ± 1.02 , respectively, p=0.001), higher fracture prevalence (70.6, 22.2, 21.8%, respectively, P<0.0001) and spinal deformity (calculated index by summing the grade of deformity for each vertebra, p<0.0001) in

Abbreviated Title: Subclinical Hypercortisolism

Version Date: 12/19/2016

patients with subclinical hypercortisolism. Fractures and spinal deformity were associated with subclinical hypercortisolism (odds ratio of 7.27, 95% CI 3.94-13.41, $p = 0.0001$) (20).

These aforementioned studies describe the natural history of subclinical hypercortisolism and report variable rates of metabolic disease prevalence in this population. Part of the reason for this variability is the difficulty and variable criteria used to diagnosing subclinical hypercortisolism. The most common tests to diagnosis subclinical hypercortisolism include lack of cortisol suppression after 1-mg overnight dexamethasone suppression test (DST), elevated urinary free cortisol (UFC) levels, loss of cortisol secretion circadian rhythm, altered cortisol and ACTH response to CRH stimulation, low basal ACTH, and/or low dehydroepiandrosterone sulfate (DHEAS). Of these tests, the most common test to screen and diagnose subclinical hypercortisolism is the 1-mg DST test. However, there is no consensus for the optimal cut-off value for suppression of cortisol (3, 21-22). The current American Association of Clinical Endocrinologists and American Association of Endocrine Surgeons medical guidelines for the management of adrenal incidentalomas recommends a cutoff of 5 $\mu\text{g/dL}$, which is associated with a sensitivity of 58% and specificity of 100% (21). Other guidelines, such as the French Society of Endocrinologist recommend a lower cutoff of 1.8 $\mu\text{g/dL}$, citing the lack of consensus (22). Researchers have also used ^{131}I -6 β -iodomethyl norcholesterol scintigraphy (IMS) to assess cortisol secretion in adrenal incidentalomas. Valli et. al. assessed the uptake of 31 patients with benign cortical neoplasms. Of the 31 patients, 19 patients had unilateral uptake and 12 patients had bilateral uptake. The patients with unilateral uptake showed lower ACTH concentrations ($p=0.0005$), higher midnight cortisol concentrations ($p=0.02$), disrupted diurnal variation of serum cortisol ($p=0.02$), and higher cortisol concentrations after a 1-mg dexamethasone suppression test ($p=0.01$). Assessing various dexamethasone suppression test cut-offs, the authors found a 2.2 $\mu\text{g/dL}$ cut-off to have a sensitivity of 100% and specificity of 67% (23). Thus, a cut-off lower than 5 $\mu\text{g/dL}$ but higher than 2.2 $\mu\text{g/dL}$ may offer a compromise in terms of sensitivity and specificity.

Since there are no overt clinical signs of cortisol excess and many of the metabolic complications are concomitantly prevalent in the elderly, an interesting study by Morelli, et. al. attempted to address diagnosis of subclinical hypercortisolism by correlating between biochemical diagnostic criteria and clinical metabolic manifestations. Biochemical data from 231 patients with unilateral adrenal incidentalomas was evaluated. The different criteria consisted of various combinations of 1-mg dexamethasone suppression test with varying cut-offs, elevated urinary fractionated cortisol and low basal ACTH. The metabolic complications evaluated included hypertension, type 2 diabetes, and vertebral fractures. The study showed having 2 out of 3 positive results from a combination of a DST cut-off value of >82.8 nmol/l (~ 3 $\mu\text{g/dL}$), elevated urinary free cortisol, and low morning ACTH (<2.2 pmol/l) to have a sensitivity of 61.9% and a specificity of 77.1% of predicting the concomitant presence of all three metabolic complications ($p=0.001$) (24). Given the current level of clinical evidence, we will use a 1-mg dexamethasone suppression test (DST) with a cut-off of 3 $\mu\text{g/dL}$ for screening and either urine free cortisol or low morning ACTH (<2.2 pmol/l) as confirmatory of subclinical hypercortisolism in this study. We will also evaluate other laboratory tests in the diagnosis of subclinical hypercortisolism.

Although there is retrospective data indicating operative treatment as beneficial, the optimal therapeutic paradigm has yet to be defined with quality evidence (1, 3). Retrospective analyses of patients who undergo adrenalectomy has been shown to be beneficial for patients with

subclinical hypercortisolism. An earlier study with a small cohort of nine patients showed that 6 out of the 8 patients with preoperative hypertension had improvement of their blood pressure postoperatively. A reduction of pharmacotherapy due to improved glycemic control was also shown in 2 out of 3 patients with preoperative diabetes. Nearly all of the patients had a reduction in their weight postoperatively (9). In another retrospective analysis of patients with subclinical hypercortisolism who either opted for adrenalectomy versus observation demonstrated significant benefit in the adrenalectomy group. In the study, 20 patients underwent operative intervention and 15 patients opted for conservative management. Baseline demographics and metabolic features were similar and statistically nonsignificant between the two groups. In the operated patients, 53% of patients had an improvement in blood pressure and 50% had improved glycemic control, whereas there was no improvement in the control group ($P < .01$) (10). Chiodini et. al. evaluated 41 patients who were diagnosed with subclinical hypercortisolism and either underwent adrenalectomy ($n=25$) or refused surgery ($n=16$). After an 18 month follow-up, a comparison of the two groups showed the adrenalectomy group to have improvement in weight (32 vs. 12.5%, $p=0.05$), blood pressure (56 vs. 0%, $p<0.0001$), and fasting glucose levels (48 vs. 0%, $p=0.001$). The blood pressure (50 vs 0%, $p<0.0001$), fasting glucose levels (37.5 vs. 0%, $p=0.001$), and LDL levels (50 vs. 20%, $p=0.05$) worsened in patients who did not have adrenalectomy (25). One of the largest studies to date, a group in Italy prospectively analyzed the outcomes of 45 subclinical hypercortisolism patients over a 15-year period. The patients were divided into operative ($n = 23$) and nonoperative ($n = 22$) groups. The prevalence of metabolic complications was similar between the two groups: diabetes (34.8% vs. 27.3%), hypertension (78.3% vs. 68.2%), hypercholesterolemia (34.8% vs. 31.8%), obesity (26.1% vs. 27.3%), and osteoporosis (21.7% vs. 27.3%). The analysis of the long-term outcome of the surgical group revealed a statistically significant improvement and/or normalization in 12 out of 18 patients with hypertension ($p=0.46$). Although statistically not significant, diabetes normalized and/or improved in 5 out of 8 patients ($p=0.619$), hypercholesterolemia normalized in 3 out of 8 patients ($p=0.619$) and the BMI normalized in 3 out of 6 patients (p value not reported). Unfortunately, the authors did not do a data comparison between the medically managed group and the operative group (1).
